5.3. Lifestyle Considerations

Prolonged exposure to natural or artificial sources of UV radiation (including sun lamps, tanning booths) is prohibited from 2 weeks prior to the baseline visit through the last study visit. When outdoors, participants will be advised to wear loose-fitting clothing that protects the treated areas from the sun.

If sunscreen, makeup, or other cosmetics have been applied to the areas to be treated, participants should wash the treatment areas with mild soap and water and pat dry before application of study cream (see Section 6.6.2).

Participants should abstain from physical activity that can cause significant sweating for approximately 2 hours following study cream application.

Use of swimming pools during the study is not recommended. If unavoidable, it is recommended that swimming should not take place within 2 hours before and after study cream application.

5.4. Screen Failures

Screen failures are defined as participants who consent to participate in the clinical study but are not subsequently entered into the study.

Tests with results that fail eligibility requirements may be repeated once during screening if the investigator believes the result to be in error. Additionally, a participant who fails screening may repeat the screening process 1 time if the investigator believes that there has been a change in eligibility status. Participants who rescreen must reconsent (if rescreened ≥ 28 days after the initial screening or ≥ 35 days after the initial screening for those participants on prior medications requiring a 4-week washout period, as described in Section 5.2, Exclusion Criterion 5b) and be assigned a new screening number. Reasons for screen failure will be recorded in the eCRF.

5.5. Recruitment Strategy and Retention of Participants

Potential study participants may be identified from the investigator's existing patient database, physician referrals, local or centralized advertisements, and direct-to-patient outreach (prescreener websites). Potential study participants may be presented with IRB/IEC-approved recruitment tools at the study site and advertisements (such as online social media platforms) before providing the written ICF. Any personal data gathered directly from respondents via prescreener websites will be collected based on affirmative participant acknowledgment of the relevant privacy policy and terms of use and affirmative participant consent (per GDPR 6.1.a) to the purpose of screening and study matching. Personal information records gathered under these

acknowledgments and consent are made available only to clinical study investigators (or other qualified staff at the clinical study site).

Following identification of a potential study participant, the investigator, delegated site staff, or referring physician will approach the potential participant and provide initial information relating to the clinical study. The investigator or their representative will follow the ICF process in Section 8.1.1 before performing any study-related procedures.

5.6. Replacement of Participants

Participants are not anticipated to be replaced during the study.

6. STUDY TREATMENT

6.1. Study Treatments Administered

Table 6 presents the study treatment information.

Table 6: Study Treatment Information

	Study Treatment 1	Study Treatment 2
Study treatment name	Ruxolitinib 1.5% cream	Vehicle
Dosage formulation	Cream	
Unit strength	1.5%	Not applicable
Route of administration	Topical	
Administration instructions	BID (morning and evening applications at least 1 hour before bedtime; optimally at equal intervals, ideally 12 hours apart, but with at least 8 hours between applications). On days of the study site visits, when the cream is applied under site staff supervision, the prior dose should be applied at least 4 hours before the visit. A thin film should be applied to all affected areas identified at baseline during the VC period and to active lesions only during the VCE period.	
Packaging and labeling	Study cream will be provided in 60-g tubes. Each tube will be labeled as required per country requirement.	
Storage	Ambient (15°C-30°C/59°F-86°F)	
Status of treatment in participating countries	Approved for AD in USA; investigational for AD in all other countries*	Not applicable

*Ruxolitinib 1.5% cream (15 mg/g 100-g tube) is approved by the EU for the treatment of nonsegmental vitiligo with facial involvement in adults and adolescents aged 12 years and older. Ruxolitinib cream does not have marketing authorization for the treatment of AD. The use of the investigational medicinal product (ruxolitinib cream) for AD is investigational and will not be in accordance with the terms of the EU marketing authorization for vitiligo.

Ruxolitinib or vehicle study cream will be supplied in 60-g tubes and applied topically as a thin film BID (optimally at equal intervals, ideally 12 hours apart but with at least 8 hours between applications, or at least 4 hours since the previous application on-site visit days when study

cream is applied under site staff supervision) to the affected areas in the morning and in the evening, with the evening application at least 1 hour before bedtime.

At the Day 1 baseline visit, an estimate of the %BSA to be treated will be used by the IRT system to calculate the number of tubes of study cream to be dispensed. All AD areas identified at the baseline visit should continue to be treated through the end of the VC double-blind period (at Week 8), even if the area begins to improve or the AD resolves completely, unless the participant meets any criteria for stopping study cream.

If there are new areas to be treated, including expansion of existing areas or development of new areas, after consultation with the investigator, study cream should be applied to these areas in addition to the areas identified at the baseline visit (up to a maximum total of 20% BSA) for the remainder of the VC period, and the percentage of BSA to be treated will be recalculated and increased accordingly. This new estimate will be entered into the IRT system to calculate the number of tubes of study cream to be dispensed. During the VC period, participants whose additional new areas to be treated in addition to the areas identified at the baseline visit exceed 20% BSA will be discontinued from study treatment and complete the ET visit.

The VCE period starts at the Week 8 visit and completes at the Week 24 visit, with the final possible application being the evening application on the day before the Week 24 visit. During the VCE period, only areas with active disease should be treated.

After completing 8 weeks of continuous treatment, all eligible participants with an adequate response, defined as achieving at least EASI50 from baseline, will continue their blinded treatment allocation and will be evaluated during an additional 16-week VCE period for durability of response. Participants will be eligible to enter the ruxolitinib 1.5% cream open-label escape arm if EASI50 is not achieved at Week 8 or if an EASI50 response from baseline is lost during the VCE period. (Note: < EASI50 must be observed at 2 consecutive visits, one of which can be an unscheduled visit, at least 1 week apart.)

The start and end dates of treatment applications will be captured by the participant. Once the lesions clear (IGA score of 0), participants should continue to apply study cream for an additional 3 days to the areas of the body where lesions were last present before discontinuing treatment. Following clearance, if a lesion recurs, treatment should be resumed at the first sign of recurrence.

At any time during the VCE period, if a participant's total AD-affected area exceeds 20% BSA, the participant will be discontinued from study treatment and complete the ET visit.

6.1.1. Study Treatment Application Guidance

Participants should remove study cream from the tube and apply the study cream with their fingertip (see [Figure 2](#)) in small amounts until all of the areas to be treated are covered by a thin, even film. Additional training will be provided in the SRM.

Figure 2: Study Cream Application Using a Fingertip

Source: DermNet New Zealand (www.dermnetnz.org).

In the clinic, the amount of study cream used will be determined by weighing a tube before and after the participant applies a thin film of study cream to the affected areas. New tubes of study cream will be provided at each visit.

Study cream should be applied in front of site staff for all on-site visits. The Day 1 baseline visit should be performed in the morning (AM). The study personnel need to ensure that they understand the quantity to be used and the application method. For all other (non-Day 1) visits, the participant should apply either of the 2 daily doses at the site, as long as the previous dose was applied at least 4 hours prior (see Section 8.4).

Study cream application does not apply to the Week 8 visit if the IGA score is 0 or to the Week 24 or ET visits.

Application instructions will be provided by the site study staff, and the participants will record their daily applications plus any missed or interrupted doses via an eDiary. Participants must not apply study cream more or less often than BID. Refer to the SRM for participant instructions for handling study cream.

6.2. Preparation, Handling, and Accountability

The investigator or designee must confirm appropriate temperature conditions (both ruxolitinib cream and vehicle cream are to be stored between 15°C and 30°C [59°F-86°F]) have been maintained during transit for all study treatments received and any discrepancies are reported and resolved before use of the study treatment.

Only participants enrolled in the study may receive study cream, and only authorized site staff may distribute study cream. The cream will be applied by the participant. Immediately after application of study cream, the hands should be thoroughly washed with soap and water. (Note: study cream is for exclusive use on the skin.) In case of accidental exposure to the eyes or mucous membranes, the cream should be immediately removed from that area and necessary supportive measures taken. Refer to the SRM for participant instructions for handling of study cream.

All study treatment cream must be stored at the investigators' sites in a secure, environmentally controlled, and monitored (manual or automated) area in accordance with the labeled storage conditions with access limited to the investigator and authorized site staff. Participants should store study cream at ambient temperature conditions.

The investigator or designee is responsible for study treatment accountability, reconciliation, and record maintenance (ie, receipt, reconciliation, and final disposition records). Inventory and accountability records must be maintained and readily available for inspection by the study monitor and are open to inspection at any time by any applicable regulatory authorities. The investigator or designee must maintain records that document the following:

- Delivery of study cream to the study site
- Inventory of study cream at the site
- Participant use of the study cream, including tube weight and counts from each supply dispensed
- Return of study cream to the investigator or designee by participants

The investigational product must be used only in accordance with the Protocol (see Section 6.1). The investigator or designee will also maintain records adequately documenting that the participants were provided the specified study cream. These records should include dates, quantities, and any available batch or serial numbers or unique code numbers assigned to the investigational product and study participants.

Completed accountability records will be archived by the site. The investigator or designee will be expected to collect and retain all used, unused, and partially used containers of study cream until verified by the study monitor (unless otherwise agreed to by the sponsor). At the conclusion of the study, the investigator or designee will oversee the destruction of any remaining study cream according to institutional SOPs. If, however, local procedures do not allow on-site destruction, shipment of the study cream back to the sponsor is allowed. In this case, the site should (where local procedures allow) maintain the investigational supply until the study monitor inspects the accountability records in order to evaluate compliance and accuracy of accountability by the investigative site. At sites where the study cream is destroyed before monitor inspection, the monitors rely on documentation of destruction per the site SOP.

Further guidance and information for the final disposition of unused study treatments are included in the study materials provided to sites.

6.3. Measures to Minimize Bias: Randomization and Blinding

All participants will be centrally assigned to study treatment using an IRT system. The system will assign study treatment in a 2:1 ratio, stratified by baseline EASI score (< 16 or ≥ 16) and geographic region (ROW vs Europe), assign the participant study number, track participant visits, randomize according to the defined parameters, maintain the blinding, and manage study cream inventory. Full details will be provided in the IRT Manual. Study treatment will be dispensed at the study visits (see Table 3 and Table 4).

At screening, participants will be assigned a unique number (randomization number) in ascending numerical order at each study site. The randomization number encodes the

participant's assignment to 1 of the 2 treatment groups in the study, according to the randomization schedule generated before the study by the sponsor's unblinded statistician and provided to IRT vendor. Each participant will be dispensed blinded study cream labeled with their unique randomization number throughout the study.

Participants and investigators will remain blinded to each participant's treatment assignment throughout the study; however, the sponsor will be unblinded after the primary database lock (see Section 10.6). Emergency unblinding will occur if an AE requires the investigator to be made aware of the participant's treatment assignment (see emergency unblinding procedures in Section 9.7).

Matching vehicle cream contains the same excipients as the active drug product, the only difference is the replacement of the active component. Hence, the use of vehicle cream maintains the blind for participants.

6.4. Study Treatment Compliance

Compliance with all study-related treatments must be emphasized to the participant by the site personnel, and appropriate steps should be taken to optimize compliance during the study. Compliance with study cream will be evaluated by the participant's adherence to the BID application regimen (evaluation of actual number vs prescribed number of applications), documented by the site staff, and monitored by the sponsor/designee. Participants will also be questioned regarding study cream application technique, missed applications, and use of any additional topical or systemic prescriptions of other products or over-the-counter products.

Qualified clinical staff will review the eDiary entries for compliance at study visits. Furthermore, the study staff should contact the participant at minimum 1 week prior to each visit during the VC period (see Table 3) and in between regularly scheduled visits during the VCE period (see Table 4) to confirm the participant's compliance with completion of the eDiary. Participants will be considered compliant with the treatment regimen if they apply at least 80% but no more than 120% of the prescribed number of applications during participation in the VC and VCE periods of the study. Participants who are noncompliant during the VC period or the VCE period (if on treatment) will be reinstructed by the investigator (or designee), and the sponsor should be consulted by the investigator for instruction on the proper handling of the participant.

Drug accountability will be assessed by documenting the quantities of study cream used between study visits (tube counts and weighing). At the first clinic visit and subsequent study visits, the amount of study cream applied is to be determined by weighing a tube before and after the participant applies a thin film of study cream to the affected areas. Participants will be instructed to bring all assigned/dispensed study cream with them to the study visits (this includes empty tubes) in order for site personnel to assess study cream accountability. Participants will be instructed to not discard/throw away any empty/used tubes.

6.5. Dose Modifications

There are no application adjustments/modifications allowed (decrease or increase in study cream strength or frequency of application) except for study cream interruption or permanent discontinuation if needed (eg, for management of an AE; see Section 6.5.1 and Section 6.5.2).

Temporary study cream interruption due to an AE could occur at any time during the study periods; however, temporary study cream interruption due to clearance of the AD lesions is only allowed during the VCE period (see Section 4.1 and Section 6.1).

6.5.1. Criteria and Procedures for Dose Interruptions and Adjustments of Study Cream

Safety concerns should be discussed with the medical monitor immediately upon occurrence or awareness to determine whether the participant should continue or discontinue study treatment.

In some circumstances, it may be necessary to temporarily interrupt treatment as a result of AEs or laboratory abnormalities that may have an unclear relationship to study cream. In the event that an AE is present only at a specific site of study cream application, treatment may be temporarily withheld only at that lesional site and continued elsewhere. This should be recorded as a dose interruption on the AE eCRF page. Except in cases of emergency, it is recommended that any findings of concern (eg, AE) be confirmed and that the investigator consult with the medical monitor before interrupting study cream applications. Additionally, the investigator must obtain approval from the medical monitor before restarting study cream after resolution of an AE. Participants who experience a recurrence of the initial AEs upon restarting the study cream may need to permanently discontinue treatment with the study cream.

Participants should be closely monitored for the development of signs and symptoms of infection during treatment with the study cream and up to the safety follow-up visit. Study cream should be interrupted if a participant develops a serious infection, an opportunistic infection, or sepsis. Study cream application should not be resumed until the infection is controlled.

Individual decisions regarding interruptions should be made using clinical judgment and in consultation with the medical monitor (whenever possible), taking into account relatedness of the AE to the study cream and the participant's underlying condition. Guidelines for interruptions of study cream related to clinically significant laboratory abnormalities are outlined in Table 7.

Table 7: Guidelines for Interruption and Restarting of Study Cream Due to Laboratory Abnormalities

Adverse Event	Action Taken
Any Grade 3 laboratory abnormality (with the exception of asymptomatic elevations in triglyceride, cholesterol, or amylase)	
 • Laboratory abnormalities should be confirmed with repeat testing within 48 hours whenever possible and immediate delivery of the laboratory results requested. • Interrupt study cream, based on clinical judgment in consultation with the medical monitor (whenever possible), taking into account the relatedness of the AE to the study cream and the participant's underlying condition. • Interruption may occur after the initial test result or may be delayed until or unless the repeat test confirms the laboratory abnormality; however, if the repeat test does confirm the laboratory abnormality, the study cream must be interrupted unless the medical monitor approves continuation. • At the discretion of the investigator, after consultation with the medical monitor, study cream application may be restarted once the AE has resolved.
Any Grade 4 laboratory abnormality	
 • Laboratory abnormalities should be confirmed with repeat testing within 48 hours whenever possible and immediate delivery of the laboratory results requested. • Interruption may occur after the initial test result. • Permanently discontinue study cream if laboratory abnormalities are confirmed and they are considered related to study cream. Study cream may also be discontinued after the initial laboratory abnormality, with approval from the medical monitor.

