6.5.2. Criteria for Permanent Discontinuation of Study Cream

Participants must permanently discontinue study cream if they meet any of the following criteria:

- Occurrence of an AE that is related to treatment with the study cream that, in the judgment of the investigator or the medical monitor, compromises the participant's ability to continue study-specific procedures or is considered to not be in the participant's best interest
- Worsening of AD that requires treatment with a prohibited concomitant medication
- Any Grade 4 laboratory abnormality (see [Table 7](#)) considered related to the study cream
- Persistent AE requiring an interruption of study cream for more than 2 weeks without resolution of the AE

See Section [7](#) for discontinuation procedures.

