
• Any safety assessments (eg, electrocardiogram, vital signs measurements), including those that worsen from baseline, considered clinically significant in the medical and scientific judgment of the investigator (ie, not related to disease progression) are to be reported as an AE.• Abnormal laboratory test results are to be reported as an AE if they are considered clinically meaningful, induce clinical signs or symptoms, require concomitant therapy, or require changes in study cream. Whenever possible, a diagnosis (eg, anemia, thrombocytopenia) should be recorded in the eCRF rather than the abnormal laboratory test result (eg, low hemoglobin, platelet count decreased).• Exacerbation of a chronic or intermittent pre-existing condition/disease, including either an increase in the frequency and/or intensity of the condition, is to be reported as an AE.• New conditions detected or diagnosed after the start of study cream administration are to be reported as an AE.• New signs and/or symptoms due to the study disease that develop after the first dose of study cream are to be captured on the appropriate efficacy CRF. Any worsening of the underlying disease that is more severe than expected for the participant's condition is to be reported as an AE.• Signs, symptoms, or the clinical sequelae of a suspected drug-drug interaction are to be reported as an AE.• Signs and/or symptoms from dose administration errors of a study cream (eg, overdose) or a concomitant medication are to be reported as an AE.• "Lack of efficacy," "disease progression," or "failure of expected pharmacological action" will not be reported as an AE or SAE. Such instances will be captured in the efficacy assessments.• A condition that leads to a medical or surgical procedure (eg, endoscopy, appendectomy) will be reported as an AE if it occurs after obtaining informed consent. If the condition is present before entering the study, then it should be captured as medical history.• Pre-existing diseases, pre-existing conditions, or new conditions with expected fluctuations in signs or symptoms should be reported as an AE only if the investigator judges the fluctuation to have worsened more than expected during study participation.

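### Table 7 lets cream restart after a Grade 3 laboratory event on consultation where Section 6.5.1 requires approval, and sets no default interruption for a confirmed Grade 4 event judged unrelated

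*Protocol*

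**What the plan says.** **Restart.** The text of Protocol Section 6.5.1 covers any adverse event (AE): "the investigator must obtain approval from the medical monitor before restarting study cream after resolution of an AE". The same section then introduces Table 7, titled "Guidelines for Interruption and Restarting of Study Cream Due to Laboratory Abnormalities". The last bullet of its Grade 3 row reads: "At the discretion of the investigator, after consultation with the medical monitor, study cream application may be restarted once the AE has resolved".

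**Interruption at Grade 3.** Table 7 first leaves interruption to clinical judgment, taking relatedness into account. Once a repeat test confirms the abnormality, however, "the study cream must be interrupted unless the medical monitor approves continuation". That line does not depend on relatedness.

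**Interruption at Grade 4.** The Grade 4 row says "Interruption may occur after the initial test result", and then "Permanently discontinue study cream if laboratory abnormalities are confirmed and they are considered related to study cream". It also lets cream be stopped for good after the first abnormal result if the medical monitor approves. It contains no restart rule. Section 6.5.2 repeats the condition that a Grade 4 abnormality leads to permanent discontinuation only if it is considered related.

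**Whether these are AEs.** Section 9.1 counts an abnormal laboratory result as an AE if, among other conditions, it should "require concomitant therapy, or require changes in study cream". An interruption of cream is such a change.

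**The concern.** There are two faults in one safety rule.

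First, approval and consultation are different controls. Under approval the monitor can refuse; under consultation the investigator decides. A site that follows the Grade 3 row of Table 7 alone can restart cream in breach of the text above it.

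Second, the more severe grade has the weaker stated rule. When a Grade 4 abnormality is confirmed and judged unrelated, nothing requires the cream to be paused and nobody has to approve its continuation. That outcome turns on the investigator's causality judgment (Section 9.3), which is made blind in the double-blind periods (Section 6.3). Section 6.5.1 itself recognizes that the relationship may be unclear.

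What is at stake is participant safety, not any efficacy estimate, power or Type I error. SAP Section 9.2.2 lists cytopenias and liver function test elevations among the AEs of interest, which are the kinds of event Table 7 governs when they are severe.

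**Working it through.** No arithmetic applies. The check is a comparison of Protocol Sections 6.5.1 (text and Table 7), 6.5.2, 7.1.1 and 9.1.

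**Step 1. Do the two restart rules cover the same event?** Yes. The left column of Table 7 is headed as adverse events, its restart bullet speaks of the AE resolving, and Section 9.1 makes a laboratory result that leads to interruption an AE. The rules cannot be separated by scope.

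**Step 2. Set the rules side by side.**

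| Situation | Section 6.5.1 text | Table 7 |
|---|---|---|
| Restart after resolved Grade 3 | Monitor approval required | Investigator decides after consulting the monitor |
| Confirmed Grade 3, related or not | Clinical judgment, consulting the monitor | Interrupt unless the monitor approves continuing |
| Confirmed Grade 4, related | Clinical judgment, consulting the monitor | Permanent discontinuation |
| Confirmed Grade 4, unrelated | Clinical judgment, consulting the monitor | No required action; interruption is optional |

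The Grade 3 row is written for Grade 3, not for Grade 3 or higher, so its default does not carry up. The role of approval also differs between the rows: at confirmed Grade 3 it is needed to continue cream, while in the Grade 4 row it appears only for stopping cream after the first result.

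**Step 3. Does another rule close the Grade 4 gap?**

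- Section 6.5.2 has 4 criteria for permanent discontinuation. Two are limited to related events (a related AE, a related Grade 4 abnormality), 1 concerns worsening of atopic dermatitis, and 1 needs an interruption of more than 2 weeks to have happened already. So 0 of 4 apply to a confirmed, unrelated Grade 4 abnormality through which cream is continued.
- Section 7.1.1 has 8 mandatory reasons to stop treatment. Six do not concern laboratory events. One, on AEs of unacceptable severity, points back to Section 6.5.2. The remaining 1, on harm to the participant, can apply but rests on the investigator's judgment.
- Sections 9.5, 9.6 and 9.6.1 (liver injury, events of clinical interest, AEs of special interest) are each marked as not applicable. Protocol Table 2 states that there is no data monitoring committee.

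No rule sets a default action for this case.

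**The case against.** The best reply on restart is that the two texts can be read together. Table 7 is labelled as guidelines and its bullet is permissive, whereas the Section 6.5.1 text is mandatory and could be taken to govern. An investigator who obtains approval satisfies both, and under either text the monitor is contacted before restart. This holds, and it narrows the gap to consult versus approve. It does not remove the fault: the Protocol never says which text prevails, Table 7 uses mandatory language of its own for confirmed Grade 3, and its title expressly claims restarting as its subject.

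On Grade 4, the reply is that a result this severe is plainly a safety concern, which Section 6.5.1 says should be raised with the monitor at once so that continuation can be decided. Section 7.2 lets the investigator withdraw a participant for safety at any time, and an event that meets the serious criteria must reach the sponsor within 24 hours whatever its cause (Section 9.4). The Grade 3 rule is also softer than it first appears, since the monitor may approve continuing. All of this is correct and makes an unmanaged case less likely. None of it supplies the default that Grade 3 has.

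The last reply is about frequency. Treatment is topical and limited to 20% of body surface area, partly to limit systemic exposure (Section 2.2.1), and AEs in the two earlier Phase 3 studies were generally Grade 1 or 2 (Section 2.3). The uncovered case needs a confirmed Grade 4 value, judged unrelated, with cream neither paused nor discussed. That is a fair point about weight, and no claim is made here that the case will be common.

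**Conclusion.** Both parts hold. Section 6.5.1 and the Grade 3 row of Table 7 give different restart rules for the same event. For a confirmed abnormality judged unrelated, Table 7 requires interruption (unless the monitor approves continuing) at Grade 3 but not at Grade 4.

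The size cannot be put as a number of events, because the documents give no Grade 3 or 4 laboratory rate. The conclusion rests only on the wording, with one reading assumed: that the Grade 3 row means Grade 3 and is not meant to include higher grades. The partial cover in Sections 6.5.1, 7.1.1, 7.2 and 9.4 limits the practical harm. This is a correction the sponsor should make because it concerns safety and is cheap, not because it threatens the trial's results.

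**What to change.** Change Table 7 in two places at the next amendment.

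1. Grade 3 row, last bullet. Replace it with: *Restart requires resolution of the AE and the medical monitor's approval.*
2. Grade 4 row. Add that if the repeat test confirms the abnormality and it is judged unrelated, "the study cream must be interrupted unless the medical monitor approves continuation", and that restart requires resolution of the AE and the monitor's approval.

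The restart clause in the second change repeats what the text of Section 6.5.1 already requires. It is worth keeping so that the table can be followed on its own without breaking the text.

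The cost is two short edits and slightly more medical monitor involvement. No visit, sample or participant is added, and the SAP does not change.
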